3.8. Analysis Visit Windows

3.8.1. Definition of Study Day

Study Day 1 is defined as the first dosing date of study drug.

Study Days are calculated relative to Study Day 1 and derived as follows:

- For postdose study days: Assessment Date – First Dosing Date + 1
- For days prior to the first dose: Assessment Date – First Dosing Date

Therefore, **Study Day 1/ First Dose Date** is the day of first dose of study drug administration, as recorded on the Study Drug Administration eCRF form.

Last Dose Date is defined as the maximum, nonmissing, nonzero dose end date of treatment recorded on the Study Drug Administration eCRF form with “Study Drug Permanently Withdrawn” box checked for participants who prematurely discontinued or completed study drug according to the Study Drug Completion eCRF.

Last Study Date is the latest of the study drug start dates and end dates, the clinic visit dates, FLU-PRO questionnaire collection date, and the laboratory visit dates, including the 28-day follow-up visit date, and the death date (if applicable, only for participants who prematurely discontinued study according to the Study Completion eCRF).

Baseline value is defined as the last value obtained on or prior to the first dose date (and time, if available) unless otherwise specified (see Section [3.8.3](#)).

3.8.2. Analysis Visit Windows

Participant visits might not occur on protocol-specified days. Therefore, for the purpose of analysis, observations will be assigned to analysis windows.

The analysis windows for vital signs and SpO₂ are provided in [Table 3-1](#) (Parts A and B) and [Table 3-2](#) (Part C).

Table 3-1. Analysis Visit Windows for Vital Signs, and SpO₂ in Parts A and B

Nominal Visit	Nominal Study Day	Visit Window Study Day	
		Lower Limit	Upper Limit
Baseline	1	(none)	1 (pre dose)*
Day 1	1	1 (post dose)	1
Day 2	2	2	2
Day 3	3	3	3
Day 4	4	4	4
Day 5	5	5	6
Day 7	7	7	9
Day 14	14	10	21
Post Day 14	28	22	(None)

* For Baseline, the upper limit includes values collected at or prior to the first dose date/time.

Table 3-2. Analysis Visit Windows for Vital Signs and SpO₂ in Part C

Nominal Visit	Nominal Study Day	Visit Window Study Day	
		Lower Limit	Upper Limit
Baseline	1	(none)	1 (pre dose)*
Day 1	1	1 (post dose)	1
Day 3	3	2	4
Day 5	5	5	6
Day 7	7	7	13
Post Day 7	14	14	(None)

* For Baseline, the upper limit includes values collected at or prior to the first dose date/time.

The analysis windows for SARS-CoV-2 viral load are provided in [Table 3-3](#) (Parts A and B) and [Table 3-4](#) (Part C).

Table 3-3. Analysis Visit Windows for SARS-CoV-2 Viral Load in Parts A and B

Nominal Visit	Nominal Study Day	Visit Window Study Day	
		Lower Limit	Upper Limit
Baseline	1	(none)	1 (pre dose)*
Day 2	2	1 (post dose)	2
Day 3	3	3	3
Day 4	4	4	4
Day 5	5	5	6
Day 7	7	7	9
Day 14	14	10	21
Post Day 14	28	22	(None)

* For Baseline, the upper limit includes values collected at or prior to the first dose date/time.

Table 3-4. Analysis Visit Windows for SARS-CoV-2 Viral Load in Part C

Nominal Visit	Nominal Study Day	Visit Window Study Day	
		Lower Limit	Upper Limit
Baseline	1	(none)	1 (pre dose)*
Day 3	3	1 (post dose)	4
Day 5	5	5	6
Day 7	7	7	9
Post Day 7	14	10	(None)

* For Baseline, the upper limit includes values collected at or prior to the first dose date/time.

The analysis windows for hematology, coagulation, and chemistry laboratory tests are provided in [Table 3-5](#) (Parts A and B) and [Table 3-6](#) (Part C).

Table 3-5. Analysis Visit Windows for Hematology, Coagulation, and Chemistry Laboratory Tests in Parts A and B

Nominal Visit	Nominal Study Day	Visit Window Study Day	
		Lower Limit	Upper Limit
Baseline	1	(none)	1 (pre dose)*
Day 3	3	1 (post dose)	4
Day 5	5	5	6
Day 7	7	7	9
Day 14	14	10	21
Post Day 14**	28	22	(None)

 - The record closest to the nominal day for that visit will be selected with the exception of viral load in which the latest record will be selected.

- If there are 2 records that are equidistant from the nominal day, the later day will be selected.
- If there is more than 1 record on the selected day, values will be selected for analysis as follows:
 - For viral load, if there is more than 1 record on the selected day, the latest value will be selected. If there are multiple records with the same time or no time recorded on the same day, the geometric mean value (copies/mL) will be taken.
 - For FLU-PRO questionnaire response, the worst severity will be taken if there is more than 1 record on the selected day. If the severity is the same, the latest record will be selected.
 - For other parameters, if there is more than 1 record on the selected day, the average will be taken for continuous data and the worst severity will be taken for categorical data, unless otherwise specified.
- For postbaseline values of PCR negative confirmation (separately by sample types):
 - Use all available data to derive negative confirmation except if there are multiple records on the same day, worst value will be used for negative confirmation for that day
 - The record closest to the nominal day for that visit will be selected.
 - If there are 2 records that are equidistant from the nominal day, the later record will be selected.
- For postbaseline values PCR for DAVG calculation:
 - All values from different days within an analysis window will be used for DAVG calculation.
 - If there is more than 1 record on a study day, the latest value will be selected. If there are multiple records with the same time or no time recorded on the same day, the geometric mean value (copies/mL) will be taken.

4. PARTICIPANT DISPOSITION

4.1. Participant Enrollment and Disposition

A summary of participant enrollment will be provided by treatment group and overall for each investigator site by study part using the Safety Analysis Set. The summary will present the number and percentage of participants enrolled. For each column, the denominator for the percentage calculation will be the total number of participants analyzed for that column.

A summary of participant disposition will be provided by treatment group and overall by study part for all screened participants. This summary will present the number of participants screened, screen failure participants who were not enrolled, participants who met all eligibility criteria but were not randomized, participants randomized, participants randomized but never treated, and participants in each of the categories listed below:

- Safety Analysis Set
- Full Analysis Set
- Modified Full Analysis Set for each sample type
- PK Analysis Set for each analyte

In addition, the number and percentage of the participants in the following categories will be summarized:

- Completed randomized treatment as recorded on the Study Drug Completion form
- Prematurely discontinuing study drug prior to completion of dosing with summary of reasons for discontinuing study drug as recorded on the Study Drug Completion form
- Completed study
- Prematurely discontinuing study

The denominator for the percentages of participants in each category will be the number of participants in the Safety Analysis Set.

No inferential statistics will be generated. A data listing of reasons for premature study drug/study discontinuation will be provided.

4.2. Extent of Study Drug Exposure

Number of doses received will be summarized as continuous and categorical variables by treatment groups including placebo group for the Safety Analysis Set. Exposure data will be listed.

4.3. Protocol Deviations

A listing will be provided for those participants who did not meet at least 1 eligibility (inclusion or exclusion) criterion. The listing will present the eligibility criterion (or criteria if more than 1 deviation) that participants did not meet and related comments, if collected.

Protocol deviations occurring after participants entered the study are documented during routine monitoring. The number and percentage of participants with important protocol deviations and the total number of important protocol deviations by deviation reason (e.g., nonadherence to study drug, violation of select inclusion/exclusion criteria) will be summarized by treatment group for the FAS. A by-participant listing will be provided for those participants with important protocol deviation.

5. BASELINE CHARACTERISTICS

5.1. Demographics and Baseline Characteristics

Participant demographic variables (i.e., age, sex at birth, race, and ethnicity) and baseline characteristics (body weight [in kg], height [in cm], body mass index [BMI; in kg/m²]) will be summarized by part and treatment group and overall using descriptive statistics (n, mean, SD, median, Q1, Q3, minimum, and maximum) for continuous variables and using number and percentage of participants for categorical variables. The summary of demographic and baseline characteristics data will be provided for the Safety Analysis Set.

In addition, age groups (< 60 vs \geq 60 years), and race groups (Asian, Black, White, and other) will be summarized by treatment group and overall.

For categorical data, the Cochran-Mantel-Haenszel (CMH) test (i.e., general association statistic for nominal data and row mean scores for ordinal data [age group]) will be used. For continuous data, the Kruskal-Wallis test will be used to compare the 3 treatment groups, and the Wilcoxon rank sum test will be used to compare the 2 treatment groups.

A by-participant demographic listing will be provided by study part and participant ID number in ascending order.

5.2. Other Baseline Characteristics

The following baseline disease characteristics will be summarized by treatment group and overall for each part using descriptive statistics:

- Duration of symptoms prior to first dose of study drug
- Duration from SARS-CoV-2 PCR/NAAT/antigen testing confirmation to first dose of study drug
- Baseline alanine aminotransferase (ALT)
- Baseline aspartate aminotransferase (AST)
- Baseline respiration rate
- Baseline SARS-CoV-2 viral Load (as a continuous variable, and a categorical variable with categories of < median and \geq median) for each sample type collected

The summary of these baseline characteristics will be provided for the Safety Analysis Set. For categorical data, the Cochran-Mantel-Haenszel (CMH) test (i.e. general association) will be used. For continuous data, the Kruskal-Wallis test will be used to compare the 3 treatment groups, and the Wilcoxon rank sum test will be used to compare the 2 treatment groups.

A by-participant listing of other baseline characteristics will be provided by study part and participant ID number in ascending order.

5.3. Additional Baseline Characteristics

Symptoms for each domain will be summarized as categories 0-4 from FLU-PRO for participants in Part C. The Cochran-Mantel-Haenszel (CMH) test (i.e. row mean scores for ordinal data) will be used to compare the 2 treatment groups.

5.4. Medical History

Any medical condition or clinically significant laboratory abnormality with an onset date before the consent form is signed and not related to a protocol-associated procedure is considered to be preexisting and should be documented as medical history. General medical history data will be collected at screening. It will be coded using the MedDRA Version 23.1. A summary table will present the percentages of participants reporting each medical history preferred term, sorted first in alphabetical order by system organ class (SOC) and then by preferred term (PT) in descending order of total frequency within SOC.

A by-participant listing of medical history will be provided by participant ID number in ascending order.

6. EFFICACY ANALYSES

6.1. Primary Efficacy Endpoint

The viral load assay for the primary analysis is: 2019-nCoV Real-Time RT-PCR Viral Load assay (v2). The assay is based on CDC's qualitative 2019-nCoV EUA Assay using primers targeting SARS-CoV-2 nucleocapsid (N) gene.

6.1.1. Definition of the Primary Efficacy Endpoint

The primary endpoint of the study is time-weighted average change from baseline to Study Day 7 (DAVG₇) in SARS-CoV-2 viral load (log₁₀ copies/mL). The DAVG₇ in SARS-CoV-2 viral load is defined as the time-weighted average between the first postbaseline value through the last available value up to Study Day 7 minus the baseline value in SARS-CoV-2 viral load. DAVG₇ is calculated using the trapezoidal rule and the area-under-the-curve (AUC) concept as follows:

$$DAVG_7 = \frac{AUC_{t_1-t_7}}{(t_7 - t_1)} - Y_0$$

The AUC between t_1 and t_n in a time (i.e., study day) versus SARS-CoV-2 viral load plot is calculated as follows:

$$AUC_{t_1-t_n} = \sum_{i=1 \text{ to } (n-1)} \frac{1}{2} (Y_i + Y_{i+1}) \times (t_{i+1} - t_i)$$

Where Y_i is the SARS-CoV-2 viral load at time t_i , t_1 is the first postbaseline time, and Y_0 is the baseline SARS-CoV-2 viral load.

For participant with SARS-CoV-2 viral load data only available up to Day x ($x < 7$), the

$$DAVG_7 \text{ is defined as } DAVG_7 = \frac{AUC_{t_1-t_x}}{(t_x - t_1)} - Y_0$$

If there is no post-baseline data, then the participant will be excluded from the analysis. If there is one post-baseline data value Y_i , $DAVG_7 = Y_i - Y_0$.

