On Days 1 through 5, assessments will include a symptom-directed physical examination. A 12-lead electrocardiogram (ECG) will be performed at Day 1. Vital signs will be measured predose and postdose. Concomitant medications and adverse events (AEs) will be documented. Laboratory samples will be obtained for safety assessments (Days 1, 3, 5) and PK assessments (Days 1, 3, 5). Nasopharyngeal, oropharyngeal swab samples and saliva samples for SARS-CoV-2 testing and possible viral resistance testing will be performed on Days 1 through 5. A chest x-ray will be performed at Day 1 to identify any pulmonary infiltrates. Forced expiratory volume

in the first second of expiration (FEV₁) will be performed daily during treatment days and will be performed both predose and 10 minutes postdose. Repeat FEV₁ should be performed at 30 minutes postdose if there is > 15% reduction in FEV₁ at 10 minutes postdose compared with the same day predose FEV₁. FEV₁ assessment may also be performed if there is a clinical concern of bronchospasm. Inhaled Remdesivir for Injection formulation or PTM will be administered at Days 1 through 5. If Day 1 assessments are performed on the same day as the screening assessments, procedures need not be repeated.

Participants will complete the adapted InFLUenza Patient-Reported Outcome (FLU-PRO[®]) questionnaire daily (Days 1-14).

On Days 7 and 14, assessments will include a symptom-directed physical examination. Vital signs will be measured, concomitant medications and AEs will be documented. Laboratory samples will be obtained for safety assessments, single PK assessment (Day 7), and nasopharyngeal and oropharyngeal swab samples and saliva samples for SARS-CoV-2 testing and possible viral resistance testing.

On Day 28, assessments will include review of AEs and concomitant medications. The Day 28 follow-up assessments may be completed by telephone.

If supported by review of at least 7-day safety data from participants in Parts A and B, then the Remdesivir for Inhalation Solution formulation will be evaluated in Part C.

Pharmacokinetic Assessments:

Sparse plasma PK assessments will be conducted in all participants at selected sites in Parts A and B. Sparse plasma PK samples will be collected at Day 1 (end of nebulization, CCI [REDACTED] and Day 3 (predose and end of nebulization).

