Up to 6 participants/group in Part A and Part B will have intensive PK assessments. Intensive PK samples will be collected at Day 1 and an additional collection, either at Day 3 or Day 5, at the following time points relative to the end of nebulization: 0 (predose), 0.25, 0.5, 0.75, 1, 1.5, 2, 4, and 24 hours post end of nebulization. An additional single PK sample will be collected on Day 7 visit for subjects who participate in the intensive PK assessments.

Study Part C:

Remdesivir for Inhalation Solution formulation or PTM will be administered Days 1 through 5 with telehealth support as needed.

On Days 1, 3, 5, and 7, assessments will include a symptom-directed physical examination. Nasopharyngeal, oropharyngeal swab samples and saliva samples for SARS-CoV-2 testing and possible viral resistance testing will be collected predose with the assistance of home nursing on Days 1, 3, 5, and 7. Vital signs will be performed predose on Days 1, 3, and 5 and on Day 7. Concomitant medications and AEs will be documented. Laboratory samples will be obtained for safety assessments predose on Days 1, 3, 5, and 7. Plasma samples will be obtained for PK assessments predose on Days 3 and 5 and Day 7 (anytime sample) in all participants.

Participants will complete the adapted FLU-PRO[©] questionnaire daily (Days 1-14).

FEV₁ will be performed daily during treatment days and will be performed both predose and 10 minutes postdose. Repeat FEV₁ should be performed at 30 minutes postdose if there is > 15% reduction in FEV₁ at 10 minutes postdose compared with the same day predose FEV₁. FEV₁ assessment may also be performed if there is a clinical concern of bronchospasm.

On Days 14 and 28, assessments will include review of AEs and concomitant medications. The Day 14 and 28 follow-up assessments may be completed by telephone.

Test Product, Dose, and Mode of Administration:

In **Part A and Part B**, the Remdesivir for Injection formulation delivered by inhalation, will be used. In **Part C**, the Remdesivir for Inhalation Solution formulation will be used.

Part A: 31 mg (nominal dose) Remdesivir for Injection administered via inhalation once daily at approximately the same time each day

Part B: 62 mg (nominal dose) Remdesivir for Injection administered via inhalation once daily at approximately the same time each day

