Part C: 39 mg (nominal dose) by mouthpiece of Remdesivir for Inhalation Solution formulation administered via inhalation once daily at approximately the same time each day

Reference Therapy, Dose, and Mode of Administration:

Placebo administered via inhalation once daily at approximately the same time each day

Criteria for Evaluation:

Safety: Proportion of participants with treatment-emergent AEs and laboratory abnormalities.

Efficacy:	Change in SARS-CoV-2 viral load will be measured. A FLU-PRO [®] questionnaire will be utilized to report COVID-19 symptom severity and duration. Disease progression from baseline will be assessed by duration and change in severity of COVID-19 clinical symptoms and need for medically attended visits (MAVs).
Pharmacokinetics:	For Parts A and B, the plasma concentrations of inhaled RDV and its metabolites will be measured, as appropriate. The following plasma PK parameters will be calculated for each analyte (RDV, GS-441524 and GS-704277), as applicable: AUC _{0-24h} , AUC _{tau} , AUC _{last} , CL _{SS/F} , t _{1/2} , V _{Z/F} , C _{max} , T _{max} , C _{last} , T _{last} , λ _Z , C _{tau} . CCI
Statistical Methods:	
No statistical sample size/power calculation was performed as the sample size of up to approximately 152 participants is deemed feasible and sufficient to provide a descriptive assessment of viral kinetics, safety and tolerability, PK and disease progression in this study.
 
Antiviral activity evaluation will be based on time weighted average change in SARS-CoV-2 viral load (defined as the AUC of viral load change divided by time between baseline to Day 7) and will be summarized by treatment group and each RDV group compared with placebo.

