3. STUDY DESIGN

3.1. Endpoints

The primary endpoint of this study is:

- Time weighted average change in SARS-CoV-2 viral load which is defined as AUC of viral load change divided by time between baseline through Day 7

The secondary endpoints of this study are:

- Proportion of participants with treatment-emergent AEs (TEAEs) and laboratory abnormalities
- Proportion of participants with TEAEs leading to study treatment discontinuation
- Composite of all-cause medically attended visits (MAVs) (medical visits attended in person by the participant and a health care professional) or death by Day 28
- Composite of COVID-19 related MAVs (medical visits attended in person by the participant and a health care professional) or death by Day 28
- Proportion of participants hospitalized by Day 28
- Characterization of the plasma concentrations of inhaled RDV and its metabolites including AUC_{0-24h} , AUC_{last} , $CL_{ss/F}$, $t_{1/2}$, $V_{z/F}$, C_{max} , T_{max} , C_{last} , T_{last} , AUC_{tau} , λ_z , and C_{tau} (Parts A and B only)
- Change in SARS-CoV-2 viral load from baseline to Day 5
- Change in SARS-CoV-2 viral load from baseline to Day 7
- Change in SARS-CoV-2 viral load from baseline to Day 14 (Parts A and B only)
- Time to negative SARS-CoV-2 polymerase chain reaction (PCR)
- Time to alleviation (mild or absent) of baseline COVID-19 symptoms as reported on the COVID-19 adapted InFLUenza Patient-Reported Outcome (FLU-PRO[®]) questionnaire

CCI

■ [REDACTED]
■ [REDACTED]
■ [REDACTED]
■ [REDACTED]

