- A value of 695 copies/ml (1/2 of the LOQ of 1390 copies/ml) will be used to calculate descriptive statistics if the datum is reported as “ $< 1390\text{cp/mL SARS-CoV-2 detected}$ ” from saliva sample.
- A value of 501 copies/ml (1/2 of the LOD of 1002 copies/ml) will be used to calculate descriptive statistics if the datum is reported as “No SARS-CoV-2 detected” from saliva sample.

Any SARS-CoV-2 viral load samples collected on or after the participants are receiving additional COVID-19 treatments (see [Appendix 2](#)) will be excluded from the viral load analysis.

Patients with negative viral load at baseline are not included in the viral load analysis.

Base 10 logarithm transformation will be used for analyzing SARS-CoV-2 viral load.

Sparse PK concentration values that are below the limit of quantitation (BLQ) will be presented as “BLQ” in the data listing.

Natural logarithm transformation will be used for analyzing concentrations. Concentration values that are BLQ will be presented as “BLQ” in the concentration data listing. For intensive PK concentration, values that are BLQ will be treated as 0 at predose time points, and one-half the value of the LOQ at postdose time points for summary purpose. For predose or postdose timepoint of sparse PK and single anytime PK, values that are BLQ will be treated as one-half the value of the LLOQ for summary purpose.

The following conventions will be used for the presentation of summary and order statistics:

- If at least 1 subject has a concentration value of BLQ for the time point, the minimum value will be displayed as “BLQ.”
- If more than 25% of the subjects have a concentration data value of BLQ for a given time point, the minimum and Q1 values will be displayed as “BLQ.”
- If more than 50% of the subjects have a concentration data value of BLQ for a given time point, the minimum, Q1, and median values will be displayed as “BLQ.”
- If more than 75% of the subjects have a concentration data value of BLQ for a given time point, the minimum, Q1, median, and Q3 values will be displayed as “BLQ.”
- If all subjects have concentration data values of BLQ for a given time point, all order statistics (minimum, Q1, median, Q3, and maximum) and summary statistics will be displayed as “BLQ.”

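### The formula in SAP 6.1.1 leaves out the interval from baseline to the first postbaseline swab, so it does not compute the primary endpoint declared in the protocol and in SAP 1.2

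*SAP*

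**What the plan says.** The declared endpoint is the same in four places. The synopsis has it "defined as the AUC of viral load change divided by time between baseline to Day 7"; Protocol 3.1, Protocol 8.1.2 and SAP 1.2 have it "defined as AUC of viral load change divided by time between baseline through Day 7".

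SAP 6.1.1 defines DAVG7 as "the time-weighted average between the first postbaseline value through the last available value up to Study Day 7 minus the baseline value". In its equation the AUC runs from t1 to t7, the divisor is (t7 - t1), and the baseline value Y0 is only subtracted. It states that t1 is the first time after baseline. With a single postbaseline value, DAVG7 is that value minus baseline.

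The swab schedule fixes what t1 is in practice. In Parts A and B, swabs and "possible viral resistance testing will be performed on Days 1 through 5", then on Day 7. In Part C they are "collected predose with the assistance of home nursing on Days 1, 3, 5, and 7".

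On record selection, SAP 3.8.3 says "All values from different days within an analysis window will be used for DAVG calculation". Tables 3-3 and 3-4 (the latter is "Analysis Visit Windows for SARS-CoV-2 Viral Load in Part C") set the Day 7 window at Days 7-9. SAP Appendix 2, item 18a, sets inconclusive results to missing for numeric summaries.

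**The concern.** Subtracting Y0 from an average of viral load is the same as averaging the change, so the two definitions differ only in the first interval. The SAP omits it from both the AUC and the divisor. One could try to read t1 as Day 1, which would restore the declared interval. The text rules that out by naming t1 as postbaseline, and the single-value rule agrees with the text. The SAP therefore conflicts with the protocol and with its own Section 1.2.

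Three things are at stake:

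- **Meaning.** A reader who knows the protocol definition will misread the reported reduction.
- **Dependence on t1.** DAVG7 uses actual study days. A missed, shifted, unscheduled or inconclusive first swab changes the score for the same viral decline.
- **Pooling.** SAP 3.2 and 6.1.3 allow ANCOVA across Parts A, B and C. The formula averages over a different span in Part C, so it can score identical declines differently by Part. The poolability check covers demographic and baseline characteristics and cannot detect this.

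A related ambiguity affects the other end. SAP 6.1.1 stops at Study Day 7, but SAP 3.8.3 uses every value in a window that runs to Day 9. Late samples are foreseeable: Protocol 6.4 gives a window of 3 days either side for the Day 7 and 14 visits in Parts A and B.

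**Working it through.** **Inputs from the documents.** Sampling days 1, 2, 3, 4, 5, 7 (Parts A and B) and 1, 3, 5, 7 (Part C). Planned arms: 36 at 1:1:1 gives 12 per arm in each of A and B; 80 at 3:1 gives 60 and 20 in C. The plan states no decline rate, SD, effect size or expected DAVG7, so there is no figure to reproduce and every rate below is an assumption.

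**Formulas.** With change Ci = Yi - Y0 and C0 = 0 at Day 1:

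- Declared: sum from i = 0 of 0.5(Ci + Ci+1)(ti+1 - ti), divided by (tn - t0).
- SAP: the same sum from i = 1, divided by (tn - t1).
- Link between them: declared = [(t1 - t0)/2 × C1 + (tn - t1) × SAP]/(tn - t0).

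**Weights on the change at each visit**

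| | Declared | SAP |
|---|---|---|
| Part C, Days 3/5/7 | 0.333, 0.333, 0.167 (sum 0.833) | 0.25, 0.50, 0.25 (sum 1) |
| A/B, Days 2/3/4/5/7 | 0.167, 0.167, 0.167, 0.25, 0.167 (sum 0.917) | 0.1, 0.2, 0.2, 0.3, 0.2 (sum 1) |

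**Linear decline of r log10/day.** Declared = 3r in every Part; SAP = 3.5r in A/B and 4r in C.

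| r | Declared | SAP, A/B | SAP, C |
|---|---|---|---|
| 0.2 | -0.60 | -0.70 | -0.80 |
| 0.3 | -0.90 | -1.05 | -1.20 |
| 0.4 | -1.20 | -1.40 | -1.60 |

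**Other shapes.** For exponential decline at rate 0.1 to 1 per day, SAP/declared falls from 1.16 to 1.12 (A/B) and from 1.32 to 1.22 (C). Rebound can remove or reverse the gap: Part C changes of -2, -1, 0 give a ratio of 1.00, and -2, -0.5, 0 give 0.90.

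**Dependence on t1** (Part C, r = 0.3, declared value -0.90 each time). SAP scores: first swab Day 2, -1.05; Day 3, -1.20; Day 4, -1.35; Day 3 missing, -1.50; Day 7 only, -1.80.

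**Day 8-9 samples** (same decline, SAP formula). Samples on Days 3/5/8 give -0.90 if Day 8 is dropped and -1.35 if it is used. Days 3/5/9 give -0.90 or -1.50.

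**Pooled comparison, no drug effect, r = 0.3, SAP formula**

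- Pooled PTM: (24 × -1.05 + 20 × -1.20)/44 = -1.118.
- 39 mg minus PTM: -1.20 + 1.118 = -0.08 (-0.05 to -0.11 for r = 0.2 to 0.4).
- 31 or 62 mg minus PTM: -1.05 + 1.118 = +0.07 (+0.05 to +0.09).
- All RDV: (48 × -1.05 + 60 × -1.20)/108 = -1.133, a difference of -0.015 (-0.01 to -0.02).

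Under the declared formula all of these are zero for linear decline.

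**Part C power** (assumed 60/20, SD 1.5, AR(1) correlation 0.5 over baseline and Days 3, 5, 7, baseline-adjusted, two-sided 5%, 77 df)

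| Effect at Days 3, 5, 7 | SAP | Declared |
|---|---|---|
| 0.4, 0.8, 1.2 | 77% | 71% |
| 0.8, 0.8, 0.8 | 77% | 80% |
| 0.8, 0.8, 0.4 | 65% | 71% |

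**The case against.** The best defence is that this is a reweighting, not a bias. Part C is the only Part with a planned within-Part test of DAVG7. Both arms share one schedule and one formula, and baseline is already a covariate. Anchoring adds no postbaseline data, and power moves either way. The SAP's formula is also fully specified, whereas the protocol gives one sentence, and the study is descriptive and unpowered. All of this stands. It limits the consequences but does not make the computed quantity the declared one.

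The pooled benefit of anchoring is also less clean than the linear case suggests. The Parts have different sampling grids, and re-anchoring does not change that. For an exponential decline of 3 log10, 39 mg minus pooled PTM is -0.094 (SAP) against +0.029 (anchored) at rate 0.5, but -0.059 against +0.062 at rate 1: the same size with the sign reversed. This stands too. Pooling is optional and conditional, and the case for change should not rest on it.

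On Day 8-9 samples, one can argue that 6.1.1 governs because it is specific to the endpoint. That is a fair reading, but 3.8.3 also addresses DAVG by name, so a programmer could go either way.

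Finally, text after SAP 6.2.1 is redacted and may declare the departure from the protocol. It cannot be said that the change is undeclared.

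**Conclusion.** The concern holds and should be fixed. By schedule the SAP formula drops 1 of 6 days in Parts A and B and 2 of 6 in Part C. The reported value is 17% and 33% larger than the declared one under linear decline at any rate, with smaller gaps for curved declines and possible reversal with rebound. These percentages are the distance between two definitions, not error against a true value; the log10 figures rest on assumed rates.

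The dependence on the first usable swab and the open rule for Day 8-9 samples are defects in their own right. The Part C comparison remains valid under the null. The pooled artefact is small, about 0.1 log10 or less under the assumptions tried.

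**What to change.** 1. In SAP 6.1.1, start the trapezoid at baseline (t0 = Day 1, C0 = 0) and divide by (tn - t0). Apply it also when there is one postbaseline value, which then scores half the change. Keep the present formula as a sensitivity analysis. Alternatively, keep the present formula as primary, restate the endpoint in SAP 1.2 to match and, unless redacted text already does so, declare the departure from the protocol.
2. State one rule for Day 8-9 samples, for example to use them only to interpolate to Day 7. In the Day 3/5/8 example the anchored formula then gives -0.90. Anchoring alone does not settle this.
3. Add a sensitivity analysis in participants with a Day 7-window sample, since neither formula reaches Day 7 when sampling stops early. SAP 3.7 excludes "Any SARS-CoV-2 viral load samples collected on or after the participants are receiving additional COVID-19 treatments", so this also leaves out those who start such treatment before their Day 7 sample. It selects on postrandomization events and can only be supportive.

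**Cost.** A few lines of text and code, no new data.

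- Reported reductions shrink, by about 25% in Part C under linear decline (3r against 4r). A constant drug effect of 0.80 from the first swab on would be reported as 0.80 × 0.833 = 0.67 in C and 0.80 × 0.917 = 0.73 in A/B.
- Early sample loss takes a larger share of the anchored value, though the log10 shortfall is the same. In Part C at 0.3/day, a last sample on Day 5 gives -0.60 against -0.90 under the SAP (33% against 25% below the full-data value); Day 3 only gives -0.30 against -0.60 (67% against 50%).
- With curved declines the anchored value still differs between Parts by about 1-5%.

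A Part term in the pooled ANCOVA is not required. Each RDV regimen exists in one Part only, so the term would raise standard errors by 30% for 39 mg: sqrt(1/60 + 1/20)/sqrt(1/60 + 1/44) = 1.30. The rise is 25% for each 12-participant arm and 39% for pooled 31 or 62 mg. It is at most an optional sensitivity analysis.
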